9.2 Background data on safety associated with experimental drugs

The clinical adverse reactions include anxiety, skin itching, rash, nausea and stomachache, which can subside spontaneously after withdrawal. A small number of patients developed mental excitement and abnormal sleep.

9.3 Handling and recording of adverse events

9.3.1 Treatment for adverse events

Inpatient

If the subject has adverse events during hospitalization, follow the following procedures:

Found adverse events in subjects, tube bed doctor or the doctor on duty shall promptly inform researchers, if necessary, can be the first symptomatic treatment, the degree of correlation between classification by research physician preliminary assessment of adverse events and drug test, and give further advice:

- ① General adverse events: can closely observe the outcome of the event or the corresponding symptomatic treatment;
- ② Important adverse events: physicians should promptly inform major researchers, and pause treatment, adjust drug dosage and targeted treatment according to the subjects' condition;
- ③ Serious adverse events: follow "9.4" for processing and reporting.
- ④ According to the patient's treatment, if the subject's injury exceeds the capacity of the research department, the relevant department should be invited to consult and assist in the treatment.

Outpatient

The adverse events that the subjects after the study, physicians should ask detailed subjects at the time of the symptoms and signs and place, the necessary explanation and

guidance on the subjects, and the degree of correlation of adverse events and give preliminary evaluation; as the subjects in the local medical institutions, contact by telephone and reception the doctor, check again the degree of adverse events and give treatment advice:

 General adverse events: initial visit to local hospital and notification of outcome of close observation;

⁽²⁾ Important adverse events: recommend returning to the hospital for treatment or to the local hospital for treatment, and timely notification of the main researchers, such as limited local hospitals, doctors should be sent to the treatment. An emergency envelope is also provided for emergency blind use (if applicable). According to the plan request, adopts the pause treatment, adjusts the medicine dosage and the symptomatic treatment and so on.

9.3.2 Record of adverse events

(1) A physician should perform a record of adverse events, including at least the description of the adverse events, the time of occurrence, the length of the termination, the frequency of attack, and the need for treatment and, if necessary, records of the treatment given.

② In the original record as far as possible with the occurrence and development of SAE records, after the treatment, and record in the CRF table, the SAE track, until we get a proper solution or stable disease or a clear reason to research, clinical drug research institutions ethics committee, unit state food and drug administration, etc. provide a final report.

9.4 Severe adverse events

9.4.1 Treatment of severe adverse events

①In case of SAE, the first visit doctor shall notify the principal investigator or other doctors to be present. If it is serious, he or she shall notify the project leader when subjects are in danger;

② As for the judgment of SAE, according to the clinical manifestations, professional standard and immediate treatment or rescue measures must be taken; if serious toxicity caused by drug overdose, the researchers decided to accelerate the excretion of drugs and take other rescue measures, try to maintain the vital signs of the patients to be as stable as possible, ECG monitoring is necessary, if necessary the first visit doctor can get help from the relevant departments.

③ Outside the hospital subjects were judged as SAE and can't come back, they were advised to timely return to hospital or go to the local hospital. The researchers should immediately notice the person in charge of the project for further treatment; as in the local hospital, made contact with the doctors, to understand the specific situation, treatment advice.

9.4.2 Severe adverse events are reported

Researchers should give immediate rescue to serious adverse events occurred in the test, whether or not it is related to the study drug. The researchers should report to the relevant provinces, autonomous regions and municipalities directly under the drug supervision and administration department and the State Food and Drug Administration in 24 hours, report to the applicant, and ethics committee. The sponsor and researchers should quickly study what happened, and try to take the necessary measures to ensure the safety and interests of subjects and report promptly to administrative departments of health and other researchers involving the same drug. If serious adverse events associated with an experimental drug, the Applicant should undertakes the costs of the rescue and treatment of the patient and the corresponding financial compensation.. The researchers must fill out a "severe adverse event report" which should record when, how, and who are reported. The bidder guarantees to meet all legal requirements.

9.4.3 Hospitalization

Adverse events leading to hospitalization or prolonged hospitalization in clinical trials should be considered as serious adverse events. Any first hospitalized (even shorter than 24 hours). Is according to comply with this standard..

Hospitalization does not include the following circumstances:

• Rehabilitation facility

- Nursing home
- Routine routine emergency room admission
- O day surgery (e.g. outpatient / day / ambulatory surgery)

Hospitalization or prolonged hospital stays unrelated to worsening adverse events are not, in themselves, serious adverse events, for example:

- Because of the original disease, there is no new adverse event, and there is no exacerbation of the original disease.
- Management for reasons of hospitalization (e.g. routine annual examination).
- Clinical setting during the clinical trial (for example, according to the requirements of the test program).
- elective hospitalization with adverse events worsening (e.g., elective cosmetic surgery).
- scheduled treatment or surgery should be performed throughout the trial program.
- admission only because of blood use.

9.5 Grading of adverse events

Mild: mild symptoms can be tolerated, does not affect activities of daily living, symptoms are transient, in the continuing use of drugs during their own relief, without treatment.

Moderate: the symptoms are obvious, affecting the daily activities of the subjects, the symptoms for a long time, can be relieved or symptomatic relief after treatment. It may interfere with the use of investigational drugs, such as reducing drug dosages or stopping medications.

Severe: the subjects suffered from impaired body function, lost normal work and living ability, and had a long duration of symptoms. They had to be stopped and properly treated before they could be relieved

9.6 Adverse events and test drug evaluation

According to the sequence between the occurrences of adverse drug evens and usage of drugs, the type of drug reaction after drug withdrawal reaction is reduced, will disappear or reappear, causality assessment of adverse events related to study drug is certainly relevant, probably, may be related, and certainly can not. The first three were considered to be relevant to the study of the drug, which was evaluated as untoward effect of drug.(ADR).

Adverse events associated with the study of drugs are as follows:

(1)Affirmation: the use of evidence for the study of drugs, the occurrence of adverse events and research, the use of drugs have a reasonable chronological order, adverse events to study drug interpretation, more reasonable than other explanations. The drug withdrawal reaction is positive, and the repeated use (if feasible) is positive.

⁽²⁾Likely related: evidence of the use of research drugs, occurrence of adverse events, and rational timing of drug use in the study. Adverse events are more reasonable in explaining drug explanations than in other explanations. Positive drug withdrawal reaction.

It may be related to the evidence of the use of research drugs, the occurrence and use of adverse events, and the timing of the study of drugs. Adverse events can also be explained by other reasons. Positive drug withdrawal reaction.

③ Perhaps irrelevant: the use of evidence for the study of drugs, the occurrence of adverse events, explained by other reasons is more reasonable. Withdrawal reactions were negative or unclear. (4) Absolutely unrelated: no use of research drugs, or the use of research drugs and adverse events unrelated to the time, or otherwise clearly lead to adverse events.

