1.1.1 Epidemiological of cerebral hemorrhage

Cerebral hemorrhage is a kind of acute onset, rapid change, serious disease, which accounts for about 10%-25% of cerebrovascular disease, disability rate and fatality rate were 70%-80%, 38%-43%, the recurrence rate was about 1 1.8%-11%. Hypertension and amyloid cerebrovascular disease are the main causes of primary spontaneous intracerebral hemorrhage, and hypertension is the most common risk factor for intracerebral hemorrhage. Cerebral hemorrhage not only has a serious impact on patients, but also brings heavy burden to society and family. The treatment of cerebral hemorrhage is complicated , which is one of the stroke which is proved by evidence-based medicine to be effective. Standardized treatment and effective integrated management can significantly reduce the fatality rate and improve the outcome of intracerebral hemorrhage.

Delayed cerebral hemorrhage is one of the important reasons for the aggravation of cerebral hemorrhage . The amount of hematoma in patients with intracerebral hemorrhage is closely related to the secondary injury of nerve function, which directly affects the prognosis of patients. Delayed cerebral hemorrhage is closely related to coagulation dysfunction. The prevention of delayed hemorrhage is an important part in the treatment of cerebral hemorrhage. The blood coagulation is initiated immediately after Acute intracerebral hemorrhage, and the coagulation process is divided into three stages: prothrombin complex formation, prothrombin activation, and fibrin formation. Synthesis of Coagulation factor FX, F II, F VII and F IX are dependent on vitamin K1. Vitamin K1 can cause the formation of prothrombin complex, clot solid, effectively blocking the vascular rupture, so that the amount of bleeding decreased. However, while controlling bleeding, the risk of thrombosis may be induced, and how to effectively control bleeding and avoid thrombosis is often a clinical problem.

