6.1.5 Test cycle

Medication for 2 days + followed up for 6 months.

7 Test procedure and plan

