(1) Analysis of program implementation: a list was adopted to summarize the entry and completion of all and each central cases, and tabulate details and the data collation of those cases which are not meet the inclusion criteria, fall off, low compliance, against therapy and drug combination, interview time beyond window.

(2) Analysis the patient compliance and the drug combination during the trail.

(3) Condition of each analysis data set: Based on the analysis of the implementation of the program, determining the data imputation of each deviated test programme case. Summarize the cases of each analysis data sets, such as per-protocol set (PPS), full analysis set (FAS), safety set (SS).

(4) Baseline equalization analysis: Compare the baseline data of demographic data, vital signs and medical history related features.

(5) Analysis of curative effect index :

1) Compare the changes of mRS score to the baseline after using the drug in 2 days, followed up with 1 month and 6 months in the two groups. The main/important therapeutic effect index will use the baseline for the covariant, considering center, operation or not after injury for analysis of covariance. The covariance analysis was performed on the change of mRS score at baseline after 6 months of follow-up. The difference between the groups and the 95% confidence interval of the mRS score difference to the baseline values after treatment in the experimental group and the placebo group was calculated by the least square method. If the 95% confidence interval between the two groups was greater than 0, the experimental group can be

thought to be superior to the placebo group, otherwise not.

2) Compare the changes of cerebral hemorrhage amount to the baseline in the two groups.

3) Compare the changes of coagulation function, platelet level and GCS score to the baseline in the two groups.

4) Compare the number of days stayed in the ICU and the hospital in the two groups.

(6) Safety analysis:

Compare the incidence and classification rate of complications, adverse events and adverse reactions during the test in the two groups, and list the details of each adverse event, such as the detailed occurrence, outcome and the relationship with drugs.

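### Section 9.6 lets an event count as an adverse drug reaction only if the withdrawal reaction is positive, leaving no route for irreversible, fatal or post-dosing events and conflicting with the definition in 9.1

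*Protocol*

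**What the plan says.** Protocol section 9.6 defines five causality grades and states that the first three, the related ones, are evaluated as ADRs. Each of those three carries a withdrawal condition:

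- Certain: "The drug withdrawal reaction is positive, and the repeated use (if feasible) is positive".
- Likely: "Adverse events are more reasonable in explaining drug explanations than in other explanations. Positive drug withdrawal reaction".
- Possible: "Adverse events can also be explained by other reasons. Positive drug withdrawal reaction".

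Only the 'perhaps irrelevant' grade is described with any other withdrawal result, and it adds a second element: "explained by other reasons is more reasonable. Withdrawal reactions were negative or unclear". The 'absolutely unrelated' grade has no withdrawal criterion. It rests on no exposure, unrelated timing or another clear cause.

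The course is short relative to follow-up (section 6.1.5): "Medication for 2 days + followed up for 6 months". The background in section 1.1.1 notes that, while bleeding is being controlled, "the risk of thrombosis may be induced". Section 9.1 defines an ADR by causal relation to the drug and does not mention withdrawal.

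SAP section 5(6) uses the grading: "Compare the incidence and classification rate of complications, adverse events and adverse reactions during the test in the two groups". It also lists each event with its relationship to the drug.

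**The concern.** A response to withdrawal is informative when a drug is given continuously and the reaction is reversible. Here dosing ends after two days. An event that starts later offers no withdrawal to observe, and a death or a completed thrombotic event cannot be expected to reverse on stopping. If a positive response is a condition of every related grade, such events are kept out of the ADR count by wording, whatever the investigator thinks of cause.

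Two outputs inherit this: the between-arm comparison of adverse reactions and the relationship column in the event listing. Attribution also matters outside the tables, because section 9.4.2 ties the applicant's treatment costs and compensation to serious events associated with the study drug.

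**Working it through.** No arithmetic applies. The check is to set the definitions in 9.6 against the possible withdrawal results and follow the outcome into the SAP.

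**Step 1: the grades.**

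| Grade in 9.6 | Withdrawal result required | Other main element | Counts as ADR |
|---|---|---|---|
| Certain | Positive (and positive re-use if feasible) | Drug is the better explanation | Yes |
| Likely | Positive | Drug is the better explanation | Yes |
| Possible | Positive | Other causes also possible | Yes |
| Perhaps irrelevant | Negative or unclear | Another cause is more reasonable | No |
| Absolutely unrelated | None stated | No exposure, unrelated timing or clear other cause | No |

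**Step 2: three kinds of event.**

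- *Reversible, and settles when the drug is stopped.* Withdrawal is positive and all three ADR grades are open. The rule works.
- *Irreversible or fatal, with onset during the course.* Improvement on stopping cannot occur, so withdrawal is negative. No ADR grade is met.
- *Onset after the second infusion.* There is nothing to withdraw, so the response is at best unclear. No ADR grade is met.

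**Step 3: where the last two kinds go.** 'Perhaps irrelevant' fits only if another cause is more reasonable. 'Absolutely unrelated' fits only if timing or another clear cause rules the drug out. An event with plausible timing and no better explanation therefore meets none of the five definitions in full. In practice it is left ungraded or put in an unrelated grade. Either way it is not an ADR.

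**Step 4: consistency with the rest of the protocol.**

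- Section 9.1 against 9.6: the first makes causal relation the test, and the second adds a condition that narrows it without saying so.
- Flow chart in 7.5: the row for complications and adverse reactions appears to run to the one- and six-month visits (the table is partly garbled in the text). Under 9.6, an event first arising then could not qualify as an adverse reaction.
- Within 9.6: the lead-in names four grades and omits 'perhaps irrelevant', while five are defined below it. In the text available to me, the possible grade has no number and 'perhaps irrelevant' carries the number 3. That may be an artefact of text conversion, but it shows why the grades that count should be named and not given by position.

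**Step 5: effect on SAP 5(6).** The rule removes the same kinds of event from both arms. If the drug raised the frequency of such events, the ADR comparison would understate the difference. Complications and adverse events are counted without reference to grade and are not touched.

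**The case against.** The strongest objection is that little depends on this. In a randomised comparison the safety inference comes from all-cause events by arm. SAP 5(6) already compares complications and adverse events as well as adverse reactions, and protocol section 8 lists coagulation and circulatory complications as outcomes. Rescue for serious events in 9.4.2 does not depend on relatedness. The reactions listed in section 9.2 are ones that settle after stopping, and for those a withdrawal criterion is workable. An investigator could also rely on 9.1 and use judgement. All of this stands and limits the point, but it does not remove it. The SAP still compares adverse reactions and lists attribution, and reliance on judgement would let centres grade the same event differently.

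Four stronger readings are tempting, and the documents do not support them:

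- *That such events automatically become 'perhaps irrelevant'.* That grade also requires a better alternative explanation, so some events fit no grade.
- *That these events can never be called drug-related under the protocol.* Section 9.1 would allow it. The accurate description is a conflict between 9.1 and 9.6.
- *That the rule hides the main expected harm.* Thrombosis is raised in the background, but section 1.3 lists allergic, infusion-rate and injection-site reactions, and 9.2 lists other reversible ones. Thrombosis is named but not ranked first.
- *That nearly all safety information is lost.* Taking six months as about 180 days, (180 − 2)/180 = 98.9% of observation falls after dosing. That is a share of calendar time and not of drug-related events, which may cluster early. Many late events would properly be judged unrelated on timing under any scale.

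**Conclusion.** The point holds as a defect in a stated rule. Every ADR-qualifying grade in 9.6 requires a positive withdrawal reaction, with no exception for irreversible, fatal or post-dosing events, and this contradicts 9.1. The conclusion assumes that 9.6 is the operative scale and is read as written. The condition is repeated in three separate definitions, which makes a single slip of translation an unlikely explanation.

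The consequence is limited to the ADR comparison and the per-event relationship listing. How many events would be affected cannot be derived, since neither document gives event rates or a sample size. It is worth correcting because the correction is specific and cheap, not because the trial's safety signal would be lost.

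**What to change.** In protocol section 9.6:

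1. For the likely and possible grades, replace the withdrawal condition with: *positive, or not assessable because dosing had ended or the event is irreversible or fatal*.
2. Remove 'unclear' as a deciding feature of 'perhaps irrelevant', so that this grade turns on whether another cause is more reasonable.
3. Align the four grades in the lead-in with the five defined, and state by name which count as ADRs, consistent with 9.1.

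In SAP section 5(6), make the all-cause comparison of adverse events and complications, with thrombotic events shown by arm, the main between-group safety comparison. The ADR comparison then becomes supportive.

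The cost is a short wording change in each document, with no change to visits or data collection. The reported ADR rate may rise in both arms.

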9.7 Outcome tracking of adverse events

Adverse events at the end of the study or not yet relieved must be followed until one of the following events occurs:

✓ By accident mitigation;

✓ Have stable event;

when it is not possible to obtain other information (subjects or accompanying worker refuse to provide other information to prove after follow-up efforts).

According to the severity of the adverse reactions, the hospital visits, outpatient visits, home visits, telephone calls, communications and other forms can be adopted.

Statistical analysis plan

1. Statistical software

Using STATA version 12.0 statistical software.

2. Special data processing

(1) Missing data: When a certain important data due to loss, miss follow-up, examination is happen, the LOCF method will be adopted to carry out the data and the secondary index will not be transferred.

(2) Outlier data: According to statistical and medical analysis, determine these data will be included or not. Sensitivity analysis was conducted for the outliers of the main targets, including two results consistent with those who did not outliers.

3. Selection of inspection level α and power of test β

(1) Difference test: With $\alpha = 0.05$ as the test standard, two-sided test was adopted, and the statistical methods, statistics and specific P values were given. $P \leq 0.05$ was considered statistically significant.

(2) Superiority test: Based on a power of 80% ($\beta = 0.2$), $\alpha = 0.025$ was conducted for the one-sided test. The difference between the groups and the 95% confidence interval of the mRS score difference to the baseline values after treatment in the experimental group and the placebo group was calculated by the least square method. If the 95% confidence interval between the two groups was greater than 0, the experimental group can be thought to be superior to the placebo group, otherwise not.

4. Statistical expression

(1) The statistical report mainly expressed in form, which was self-evident. It had the title, the heading and the number of cases, the necessary remarks and the text of statistical results and the description of data results.

(2) Descriptive statistics: The measurement data is described by mean number, standard deviation, maximum value, minimum value, 95% confidence interval, median, Q1 and Q3. The enumeration data is described by frequency (constituent

ratio), and corresponding statistics and P value are calculated.

(3) Inferential statistics: Measurement data were compared between groups by analysis of variance or K-W rank-sum test according to the distribution pattern. Enumeration data were compared between groups by R*C Chi-squared test and Fisher exact test. The ranked data was tested by CMH. The main/important therapeutic effect index will use the baseline for the covariant, considering center, operation or not after injury for analysis of covariance.

5. Specific statistical analysis content

(1) Analysis of program implementation: a list was adopted to summarize the entry and completion of all and each central cases, and tabulate details and the data collation of those cases which are not meet the inclusion criteria, fall off, low compliance, against therapy and drug combination, interview time beyond window.

(2) Analysis the patient compliance and the drug combination during the trail.

(3) Condition of each analysis data set: Based on the analysis of the implementation of the program, determining the data imputation of each deviated test programme case. Summarize the cases of each analysis data sets, such as per-protocol set (PPS), full analysis set (FAS), safety set (SS).

(4) Baseline equalization analysis: Compare the baseline data of demographic data, vital signs and medical history related features.

(5) Analysis of curative effect index :

1) Compare the changes of mRS score to the baseline after using the drug in 2 days, followed up with 1 month and 6 months in the two groups. The main/important therapeutic effect index will use the baseline for the covariant, considering center, operation or not after injury for analysis of covariance. The covariance analysis was performed on the change of mRS score at baseline after 6 months of follow-up. The difference between the groups and the 95% confidence interval of the mRS score difference to the baseline values after treatment in the experimental group and the placebo group was calculated by the least square method. If the 95% confidence interval between the two groups was greater than 0, the experimental group can be

thought to be superior to the placebo group, otherwise not.

2) Compare the changes of cerebral hemorrhage amount to the baseline in the two groups.

3) Compare the changes of coagulation function, platelet level and GCS score to the baseline in the two groups.

4) Compare the number of days stayed in the ICU and the hospital in the two groups.

(6) Safety analysis:

Compare the incidence and classification rate of complications, adverse events and adverse reactions during the test in the two groups, and list the details of each adverse event, such as the detailed occurrence, outcome and the relationship with drugs.

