7.3 Follow-up visit

1 months (+ 3 days) and 6 months (= 3 days) after the onset of intracerebral hemorrhage: the researchers performed a mRS score using telephone follow-up.

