7.5.3 Medication and treatment are permitted

(1) The other combined diseases without affecting the curative effect and safety evaluation, can be symptomatic medication, but it must be the case report form to record the medicine general or other treatment, dosage, reason, use frequency and time etc, so as to summarize, analyze and report.

⁽²⁾The follow-up period can use cognitive rehabilitation methods, including occupational therapy, implicit memory rehabilitation, errorless learning, cognitive neuropsychological rehabilitation, rehabilitation and computer assisted cognitive rehabilitation, virtual remote control via the Internet, and the electromagnetic stimulation, should be recorded in detail in CRF.

⁽³⁾The combination drugs used for adverse events during the trial should be recorded in CRF.

8 Therapeutic evaluation standard

Main outcome measures: the amount of intracerebral hemorrhage (0d, 1D, 3D, 7D) at each time after the onset of disease.

Main outcome measures: (1) the amount of the time changes in blood coagulation, platelet levels and GCS scores after the onset (0d, 1D, 3D, 7D); (2) days in ICU; (3) the total hospitalization days; (4) complications including neurological complications, complications, blood coagulation circulatory complications after cerebral hemorrhage; (5) 1m and 6m mRS score.

9 Safety evaluation

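### LOCF is the only stated method for missing important data: a survivor missed at month 6 keeps the month-1 mRS, which can bias or dilute the 6-month comparison, and no missing-data sensitivity analysis is planned

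*SAP*

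**What the plan says.** SAP section 2(1) covers loss, missed follow-up and missed examinations alike ("When a certain important data due to loss, miss follow-up, examination is happen") and gives one method: "the LOCF method will be adopted to carry out the data and the secondary index will not be transferred". Section 2(2) plans a sensitivity analysis for outliers. Nothing similar is planned for missing values, and no missing-data assumption is stated.

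The method reaches these outcomes:

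- **mRS.** The superiority claim in SAP sections 3(2) and 5(5) rests on 6-month mRS: "The covariance analysis was performed on the change of mRS score at baseline after 6 months of follow-up". After discharge, mRS is scheduled only at months 1 and 6, when "the researchers performed a mRS score using telephone follow-up" (Protocol 7.3). SAP 5(5) also names an earlier score: "Compare the changes of mRS score to the baseline after using the drug in 2 days, followed up with 1 month and 6 months".
- **CT volume.** Protocol section 8 opens with "Main outcome measures: the amount of intracerebral hemorrhage (0d, 1D, 3D, 7D) at each time after the onset of disease". A second list under the same heading contains "5) 1m and 6m mRS score". SAP 5(5) lists volume only as a further comparison.

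Two other provisions bear on the point. Protocol 4.4 rejects subjects who have no further visit on record. SAP 5(3) leaves the imputation of deviating cases to be decided after trial conduct has been reviewed, and gives no method.

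**The concern.** LOCF sets every change after the last observation to zero and then analyses the filled value as if it had been measured. Disability after a haemorrhage can change between month 1 and month 6, and haematoma volume can grow or resorb between scans. The carried value is therefore likely to be wrong in a systematic direction.

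For mRS this acts on the outcome that decides superiority. For volume it acts on the question the trial asks, because the purpose in Protocol section 2 is to see whether K1 prevents an increase in haemorrhage, and a carried-forward scan records no increase by construction.

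If the arms lose different shares of patients, the error does not cancel and appears as a treatment difference. If they lose equal shares but part of the effect arises after the last contact, the estimate shrinks. With no missing-data sensitivity analysis, the report could not show how far the result depends on this rule.

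**Working it through.** **Figures in the plan.** The SAP gives one-sided alpha 0.025, two-sided alpha 0.05 and power 80%. Both alphas correspond to z = 1.960. Sample size, SD, effect size and loss rate are not stated, so the power cannot be reproduced and every input below, apart from alpha, is an assumption.

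**Step 1. Bias formula.** Let pT and pC be the shares carried forward in the K1 and control arms, and dT and dC the mean true change after last contact. LOCF replaces d by 0 for those patients, so the bias in the K1-minus-control mean change is

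-(pT x dT - pC x dC).

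- Equal loss and parallel change (pT = pC, dT = dC): the bias is 0.
- Unequal loss and a common change d: the bias is -(pT - pC) x d. With recovery (d negative) and more loss in the control arm, it favours K1. With more loss in the K1 arm, the sign reverses.

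**Step 2. mRS with no true effect.** Assumptions: recovery of 0.5-1.0 points after last contact, and loss rates 5 or 10 percentage points apart.

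- 5-point gap: 0.05 x 0.5 = 0.025 to 0.05 x 1.0 = 0.05 points.
- 10-point gap: 0.10 x 0.5 = 0.05 to 0.10 x 1.0 = 0.10 points.

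**Step 3. Effect on the one-sided 2.5% error.** Assume SD 1.8. SE = 1.8 x sqrt(2/n), which is 0.161 at 250 per arm and 0.255 at 100 per arm. The error is 1 - Phi(1.960 - bias/SE) when the bias favours K1, and 1 - Phi(1.960 + bias/SE) when it goes against K1.

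| Per arm | Gap | Bias (points) | Error if bias favours K1 | Error if bias is against K1 |
|---|---|---|---|---|
| 250 | 5 points | 0.025-0.05 | 3.6-5.0% | 1.7-1.2% |
| 250 | 10 points | 0.05-0.10 | 5.0-9.0% | 1.2-0.5% |
| 100 | 10 points | 0.05-0.10 | 3.9-5.9% | 1.6-0.9% |

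The same bias matters more in a larger trial, because the SE is smaller.

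**Step 4. Simulation check.** Assumptions: no true effect, 200 per arm, loss 5% in the K1 arm and 20% in the control arm, mean change from month 1 to month 6 of -1.0, and 3000 runs. LOCF gave a mean difference of -0.15, matching the formula (0.15 x 1.0), and a two-sided error of 15.1%. Predicting month 6 from month 1 within each arm gave a difference of 0.00 and an error of 4.4%.

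**Step 5. Dilution with equal loss.** If half the effect is present at month 1 and 20% of each arm is carried forward, the estimate is 0.8 + 0.2 x 0.5 = 0.90 of the true effect. If the whole effect arises later, an effect of -0.30 becomes -0.30 x 0.80 = -0.24.

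**Step 6. CT volume, if it is a main outcome.** Assume a mean change of 3-5 mL after the last scan, and scans missed in 5% of one arm and 20% of the other. The spurious difference is 0.15 x 3 = 0.45 to 0.15 x 5 = 0.75 mL. Its sign depends on whether volume is growing or resorbing and on which arm misses more scans.

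**The case against.** **Scope.** A reader might infer that both mRS and volume will certainly be carried forward. The documents do not support that. LOCF excludes secondary indices, the protocol puts volume first, and the SAP tests superiority on mRS. Whichever outcome is ruled secondary is left as missing. This objection stands, but one main outcome remains under LOCF either way.

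**Early losses.** A reader might also infer that a survivor lost before month 1 always receives an in-hospital mRS. That is not established. Protocol 4.4 may reject such patients, and the in-hospital score appears only in the SAP: the flow chart, which is broken in the text available, shows mRS only at months 1 and 6. Protocol 4.5.3 also asks for a final examination at withdrawal, which may reduce missing data. LOCF therefore mainly reaches losses after month 1 and missed scans.

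**Unequal loss.** The tempting reading is that loss will differ because staff know the arm. The documents say the trial is single blind but do not spell out which staff are unblinded, treatment lasts two inpatient days, and no loss rate is given. Unequal loss is possible but not shown.

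**Magnitude.** No single error figure should be taken as the size of the problem. The 5.0-9.0% row is one slice of assumed inputs, smaller gaps or trials give less, and equal loss with parallel trends gives none.

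None of this removes the rule itself. The discretion in SAP 5(3) is no safeguard, because no method is attached to it.

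**Conclusion.** The point holds within limits. The SAP states a rule that makes the 6-month mRS comparison, and the volume comparison if volume is a main outcome, biased under unequal loss and diluted when an effect arises late. It also plans nothing that would reveal this. The defect is the stated method itself, not a missing detail.

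Under the assumptions in the working (SD 1.8, recovery 0.5-1.0 points, loss gap 5-10 percentage points), the one-sided error at 250 per arm is about 3.6-9.0% if the bias favours K1 and below 2.5% if it goes against K1. The true size and direction cannot be determined from the documents. The conclusion concerns survivors and missed scans. How deaths enter either outcome is a separate gap, and an important one given the background fatality of 38%-43% in Protocol 1.1.1. The change should be made before the data are analysed.

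**What to change.** Replace LOCF as the primary method, and say in the SAP which outcomes are main and how Protocol 4.4 fits with the missing-data rule.

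- **6-month mRS in survivors:** multiple imputation by arm from baseline mRS and all earlier mRS, operation or not, centre, age, GCS and day-0 volume, pooled by Rubin's rules. This includes every variable in the planned ANCOVA (baseline, centre, operation), which the imputation model must not omit.
- **CT volume:** a repeated-measures mixed model on all observed scans, with arm by day, baseline volume and centre. Because Protocol 6.1.4 allows surgical removal of the haematoma, which changes volume directly, add a sensitivity analysis for evacuation.
- **Sensitivity:** keep LOCF as a sensitivity analysis, and add a tipping-point analysis that shifts the imputed values by a delta until the conclusion changes.
- **Deaths:** do not treat values missing because of death as missing at random. State a separate rule.

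The cost is SAP wording, some programming and slightly wider confidence intervals. No extra patients or visits are needed.
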